4.4 Replacement of Subjects

Subjects who are withdrawn from the study for reasons other than suspected study drug-related AEs may be replaced at the Investigator's discretion.

4.5 Termination of Trial

The Investigator has the right to terminate this study at any time, and will notify the IRB/IEC of premature termination in writing.

Events that may trigger premature termination of the study include, but are not limited to non-compliance with the protocol, slow recruitment, or change in development plans for the study drug.

5. STUDY DRUG

5.1 Description of Study Drug

5.1.1 Active Pharmaceutical Ingredient

The study drug is levetiracetam (LEV). LEV is an antiepileptic drug belonging to the 'racetam' class of drugs that share a pyrrolidone nucleus. The chemical name of levetiracetam, is (-)-(S)-a-ethyl-2-oxo-1-pyrrolidine acetamide. LEV has a molecular weight of 170.21 and a molecular formula of C₈H₁₄N₂O₂.

5.1.2 Drug Product

The dosage form of the study drug product is an oral capsule. The inactive ingredients for both the active drug and the placebo are corn starch, croscarmellose sodium, hypromellose, magnesium stearate, polyethylene glycol, povidone, and titanium dioxide. A single dosage (125 mg) of LEV will be used for this trial.

5.1.3 Packaging and Labeling

Teva will supply the study drug for this trial. The Investigational Site pharmacists will not be blinded to the study drug. The study drug (active or placebo) will be packaged into 4-week supply blister packs that indicate twice-a-day dosing. The blister packs will look equivalent between active drug and placebo. Each 4-week supply will be labeled to indicate the participant and the phase of the cross-over study for which they are designated.

5.1.4 Storage and Handling

At the Investigational Site, the investigational study drug will be stored in a locked, secure area to prevent unauthorized access. The study drug will be stored in the provided packaging out of direct sunlight and at controlled room temperature (65 to 77°F; 18 to 25°C).

5.2 Randomization

This is a randomized, double-blinded, placebo-controlled crossover study. Subjects will be assigned to a treatment sequence (Group A or B) according to a randomization process. Only subjects that meet all eligibility criteria at the initial screening will be randomized to treatment. Randomization will take place on Day 1 after completion of screening.

A computer-generated randomization schedule will be used for assigning the sequence in which subjects are assigned to treatment sequence (Group A or B). Randomization will be performed four participants at a time to ensure relatively equal distributions of participants into the two groups at all phases of the trial and in case the trial is terminated prior to reaching goal enrollment. The Investigational Site pharmacist will be responsible for generating and maintaining the

randomization schedule, and will assign a randomization code to each subject upon enrollment.

5.3 Preparation and Administration of Study Drug

The Investigational Site pharmacists in the UCSF Drug Product Services Laboratory will compound LEV tablets into 125 mg oral capsules. Placebo capsules will be prepared in the same way, using the inactive ingredients of the LEV tablets. All doses of study drug (placebo and active) will be self-administered by the participant or administered by the participant's caregiver.

All subjects will take the study drug (placebo or active) twice a day for 4 weeks, followed by a 4-week washout period during which time they will not take any study medications, followed by a second 4-week treatment period during which they will take whichever study drug (placebo or active) was not taken during the first treatment phase.

5.4 Measuring Subject Compliance

Investigational Site staff will ascertain compliance through weekly contact with the study participants during treatment phases, and by checking for empty blister packs at the end of each treatment phase. Blood LEV levels will be collected at study days 1, 29, 57, and 85 and sent to Quest Diagnostics. The LEV levels will not be disclosed to the study investigators during the active trial, but will be reviewed at the end of the study to determine drug compliance for each participant.

5.5 Drug Accountability

In accordance with current Good Clinical Practice (GCP), the Investigational Site will account for all study drug supplies. Details of receipt, storage, administration, and return or destruction will be recorded in the study drug accountability record according to the standard operating procedure of the Investigational Site.

Study drug will only be dispensed to subjects randomized to treatment under this protocol, and only as directed by this protocol. Administration of study drug will be accurately recorded in each subject's source documents.

5.6 Concomitant Medications

All medications (or treatments) other than study drug taken or received by the subject at any time during the study from the first dose of study drug through the final study visit assessment will be considered concomitant medications. Use of all concomitant medications, including any change in therapy, must be recorded and updated in the source documentation.

Subjects are not to take any other study drugs or investigational drugs beginning 30 days prior to the first dose of study drug and continuing until completion of the study (final study visit).

FDA-approved AD medications are allowed as long as the dose is stable for at least 30 days prior

to screening and at least 60 days prior to study day 1. Other medications (except those listed above) are allowed as long as the dose is stable for 30 days prior to screening. All drugs taken during the two months prior to screening, as well as between screening and baseline (Day 1) should be recorded.

All intercurrent medical conditions will be treated at the discretion of the Investigator according to acceptable community standards of medical care.

6. SCHEDULE OF EVENTS

The schedule of events is provided in tabular format in Appendix B and is summarized below by study visit.

6.1 Screening

Subjects will initially be screened for any previous or current history of the following exclusion criteria:

1. Korsakoff's syndrome
2. Alcohol or substance abuse preceding dementia symptoms & still present within 5 years of onset
3. Head trauma with persistent deficits
4. CNS lesions deemed to be clinically significant
5. Epilepsy/seizure disorder developing > 5 years before onset of cognitive symptoms
6. Hydrocephalus
7. Intracerebral hemorrhage
8. Ischemic vascular dementia
9. Multiple sclerosis or other demyelinating disease
10. Encephalitis or meningitis
11. Untreated B12 deficiency
12. Untreated hypothyroidism
13. Untreated syphilis
14. Positive HIV status
15. Renal insufficiency requiring dialysis
16. Symptomatic liver disease
17. Severe periventricular white matter disease or greater than grade 4 white matter lesions
18. Lacunar infarcts deemed to be clinically significant.
19. Cortical stroke
20. Respiratory condition requiring oxygen
21. Significant systemic medical illness such as cancer requiring chemotherapy or endstage cardiac insufficiency

Each subject will be provided with an informed consent form (ICF) describing the study and will have any questions answered. Subjects that consent to participate in the study will undergo the following assessments:

1. Blood test for vitamin B12, thyroid stimulating hormone (TSH), complete blood count with differential (CBC diff), chemistry-7, coagulation tests [prothrombin time (PT), partial thromboplastin time (PTT), and International Normalized Ratio (INR)], and prolactin. Vitamin B12 and TSH may be excluded if recorded in the previous year, and CBC diff and coagulation tests if recorded in previous 90 days.
2. Mini mental state exam (MMSE). The MMSE (Folstein et al. 1975) will be used to evaluate the

cognitive function of subjects. Refer to the referenced publication for details regarding the exam.

3. Clinical Dementia Rating.
4. Lumbar puncture for subjects in whom amyloid positron emission tomography (PET) imaging is not already completed or scheduled. Cerebral spinal fluid (CSF) will be collected for measurement of cell count with differential, glucose, total protein, and CSF biomarkers of AD. This CSF test will not be a requirement for enrollment in the treatment study.
5. Clinician Assessment of Fluctuation and One Day Fluctuation Assessment.
6. Overnight video-EEG, including 3 minutes of hyperventilation and 7 minutes of post-hyperventilation resting-state activity, and 60-minute resting-state M/EEG comprised of 50 minutes of resting-state activity, 3 minutes of hyperventilation, and 7 minutes of post-hyperventilation resting-state activity. The EEG and M/EEG will be read by epileptologists who will note whether there is any epileptiform activity (spikes and sharp waves) and identify the spikes and sharp waves for quantitation.

6.2 Sharing of experimental research test results with subjects or their care providers

Written reports of the overnight video-EEG or M/EEG will be faxed or mailed to the subject's primary care provider in all cases where epileptiform activity is detected and in other cases where clinical follow-up is warranted. The purpose of sending these reports is to alert their health care provider to any abnormal results that could prompt further medical workup. The significance of any abnormal findings will be explained in a letter, written by [name], or by phone. Also, [name] will contact primary care physicians when the results of the study indicate the need for expedited medical workup. There are currently no clinical guidelines on whether to treat subclinical epileptiform activity with antiepileptic medications. However, the subject and their care provider will be given an opportunity to consider whether to start a medication for subclinical epileptiform activity in lieu of participating in this clinical treatment trial.

6.3 Study Day 1

Eligible subjects will return to clinic on the morning of Day 1. Prior to enrollment, to confirm that the subject continues to meet eligibility criteria, subjects will be asked to provide an updated medical history and to list any new medications taken since initial screening visit.

Subjects that continue to meet all eligibility requirements after the above baseline assessments will be enrolled in the study. The subjects will then undergo the following assessments:

1. Obtain vital signs
2. NIH EXAMINER
3. Stroop Test

4. ADAS-cog
5. Virtual Route Learning Test
6. ADCS-ADLs
7. ADCS-CGIC baseline assessment
8. CDR-SOB
9. NPI
10. Clinician Assessment of Fluctuation
11. One Day Fluctuation Assessment
12. 60-minute resting M/EEG, including 3 minutes of hyperventilation and 7 minutes of post-hyperventilation resting activity
13. 30-minute M/EEG to measure neural activity during cognitive stimulation
14. Virtual Route, 4-hour recall

At the end of the day, subjects will be randomized to treatment. Subjects will be given a month's supply of the study drug (placebo or active) in a blister pack with daily dividers and provided instructions on drug dosing. A packet insert and Frequently Asked Questions guide about LEV will be provided. The subjects will be instructed to begin the first dose that evening. Subjects will be given a diary to record any adverse events (AEs) or concomitant medications taken between visits.

Subjects or informants will be contacted weekly between study day 1 and 29 for general safety assessments.

6.4 Study Day 29

On the morning of study day 29, subjects will return to clinic for the following assessments:

1. Obtain vital signs
2. Review of diary for any recorded AEs or concomitant medications taken between visits.
3. Review of medication blister pack to count and verify number of pills taken since the previous visit
4. Collection of blood samples for determination of LEV and prolactin levels
5. NIH EXAMINER
6. Stroop Test
7. ADAS-cog
8. Virtual Route Learning Test
9. ADCS-ADLs
10. ADCS-CGIC
11. CDR-SOB
12. NPI
13. Clinician Assessment of Fluctuation
14. One Day Fluctuation Assessment
15. 60-minute resting M/EEG, including 3 minutes of hyperventilation and 7 minutes of post-hyperventilation resting activity
16. 30-minute M/EEG to measure neural activity during cognitive stimulation

17. Virtual Route, 4-hour recall

At the end of the day, the subjects will be instructed to begin a four-week break period (washout) during which time they will take no study medications.

6.5 Study day 57

On the morning of study day 57, subjects will return to clinic for the following assessments:

1. Obtain vital signs
2. Review of diary for any recorded AEs or concomitant medications taken between visits.
3. Collection of blood samples for determination of LEV and prolactin levels
4. NIH EXAMINER
5. Stroop Test
6. ADAS-cog
7. Virtual Route Learning Test
8. ADCS-ADLs
9. ADCS-CGIC (new baseline assessment)
10. CDR-SOB
11. NPI
12. Clinician Assessment of Fluctuation
13. One Day Fluctuation Assessment
14. 60-minute resting M/EEG, including 3 minutes of hyperventilation and 7 minutes of post-hyperventilation resting activity
15. 30-minute M/EEG to measure neural activity during cognitive stimulation
16. Virtual Route, 4-hour recall

At the end of the day, subjects will be given a month's supply of the study drug in a blister pack with daily dividers and provided instructions on drug dosing. The subjects will be instructed to begin the first dose that evening.

Subjects or informants will be contacted weekly between study day 57 and 85 for general safety assessments.

6.6 Study day 85

On the morning of study day 85, subjects will return to clinic for the following assessments:

1. Obtain vital signs
2. Review of diary for any recorded AEs or concomitant medications taken between visits.
3. Review of blister pack to count and verify number of pills taken since the previous visit
4. Collection of blood samples for determination of LEV and prolactin levels

5. NIH EXAMINER
6. Stroop Test
7. ADAS-cog
8. Virtual Route Learning Test
9. ADCS-ADLs
10. ADCS-CGIC
11. CDR-SOB
12. NPI
13. Clinician Assessment of Fluctuation
14. One Day Fluctuation Assessment
15. 60-minute resting M/EEG, including 3 minutes of hyperventilation and 7 minutes of post-hyperventilation resting activity
16. 30-minute M/EEG to measure neural activity during cognitive stimulation
17. Virtual Route, 4-hour recall

6.7 Duration of Participation

The total duration of participation for subjects in this study will be up to 18 weeks (first screening visit through final follow-up visit).

7. ASSESSMENT OF SAFETY

LEV is an FDA-approved medication, and an investigational new drug (IND) exemption was obtained for this study from the FDA (IND 120562) in accordance with IND regulations 21 CFR 312.2(b)(4). Safety will be assessed primarily based on adverse events (AEs). Secondary safety assessments will include ADAS-cog, ADCS-ADL, and NPI.

7.1 Safety Reporting and Adverse Events

7.1.1 Definitions

7.1.1.1 Adverse Event

An AE is defined in 21 Code of Federal Regulations (CFR) 312.32(a) as follows:

Any untoward medical occurrence associated with the use of a drug in humans, whether or not considered drug related.

An AE (also referred to as an adverse experience) can be any unfavorable and unintended sign (e.g., an abnormal laboratory finding), symptom, or disease temporally associated with the use of a drug, and does not imply any judgment about causality. An AE can arise with any use of the drug (e.g., off-label use, use in combination with another drug) and with any route of administration, formulation, or dose, including an overdose.

7.1.1.2 Serious Adverse Event

A serious adverse event (SAE) is defined in 21 CFR 312.32(a) as follows:

An AE or suspected adverse reaction is considered “serious” if, in the view of either the investigator or sponsor, it results in any of the following outcomes:

- death
- a life-threatening AE
- inpatient hospitalization or prolongation of existing hospitalization
- a persistent or significant incapacity or substantial disruption of the ability to conduct normal life functions
- a congenital anomaly/birth defect

Important medical events that may not result in death, be life-threatening, or require hospitalization may be considered serious when, based upon appropriate medical judgment, they may jeopardize the patient or subject and may require medical or surgical intervention to prevent one of the outcomes listed in this definition. Examples of such medical events include allergic bronchospasm requiring intensive treatment in an emergency room or at home, blood

dyscrasias or convulsions that do not result in inpatient hospitalization, or the development of drug dependency or drug abuse.

An AE or suspected adverse reaction is considered “life-threatening” if, in the view of either the investigator or sponsor, its occurrence places the patient or subject at immediate risk of death. It does not include an AE or suspected adverse reaction that, had it occurred in a more severe form, might have caused death.

7.1.2 Severity of Adverse Events

The severity of AEs will be graded according to National Cancer Institute (NCI) Common Terminology Criteria for Adverse Events (CTCAE) version 4.0. A copy of CTCAE version 4.0 can be downloaded from the Cancer Therapy Evaluation Program (CTEP) web site (http://ctep.cancer.gov/protocolDevelopment/electronic_applications/ctc.htm).

The severity of AEs not classified by the above referenced toxicity grading scale will be categorized using the following definitions:

Mild (Grade 1):	Asymptomatic or mild symptoms; clinical or diagnostic observations only; intervention not indicated
Moderate (Grade 2):	Minimal, local or noninvasive intervention indicated; limiting age-appropriate instrumental activities of daily living (e.g., preparing meals, shopping for groceries or clothes, using the telephone, managing money, etc.)
Severe (Grade 3):	Severe or medically significant but not immediately life-threatening; hospitalization or prolongation of hospitalization indicated; disabling; limiting self-care activities of daily living (e.g., bathing, dressing and undressing, feeding self, using the toilet, taking medications, and not bedridden)
Life-threatening (Grade 4):	Life-threatening consequences; urgent intervention indicated
Death (Grade 5):	Death related to AE

7.1.3 Relationship of Adverse Events to the Study Drug

The relationship of AEs to the study drug will be classified as one of the following:

- 1. Adverse reaction:** Any AE caused by a drug. Adverse reactions are a subset of all suspected adverse reactions where there is reason to conclude that the drug caused the event.
- 2. Suspected adverse reaction:** Any AE for which there is a reasonable possibility that the

drug caused the AE. For the purposes of IND safety reporting, “reasonable possibility” means there is evidence to suggest a causal relationship between the drug and the AE. A suspected adverse reaction implies a lesser degree of certainty about causality than adverse reaction, which means any AE caused by a drug.

Examples of the types of evidence that would suggest a causal relationship between the drug and the AE are as follows:

- A single occurrence of an event that is uncommon and known to be strongly associated with drug exposure (e.g., angioedema, hepatic injury, Stevens-Johnson Syndrome)
- One or more occurrences of an event that is not commonly associated with drug exposure, but is otherwise uncommon in the population exposed to the drug (e.g., tendon rupture)
- An aggregate analysis of specific events observed in a clinical trial (such as known consequences of the underlying disease or condition under investigation or other events that commonly occur in the study population independent of drug therapy) that indicates those events occur more frequently in the drug treatment group than in a concurrent or historical control group

3. **Unrelated:** AE for which there is evidence that the AE definitely has an etiology other than the drug.

7.1.4 Expectedness of Adverse Events

An unexpected AE is defined in 21 CFR 312.32(a) as follows:

An AE or suspected adverse reaction is considered “unexpected” if it is not listed in the investigator brochure or is not listed at the specificity or severity that has been observed; or, if an investigator brochure is not required or available, is not consistent with the risk information described in the general investigational plan or elsewhere in the current application, as amended.

The LEV package insert will serve as the investigator brochure for this study.

7.1.5 Monitoring of Adverse Events

AEs will be monitored continuously during the study. Subjects will be instructed to report all AEs experienced during the study, and subjects will be assessed for the occurrence of AEs throughout the study. Subjects will be given a diary to record any AEs between visits. During the treatment period study staff will be available by telephone in case of unexpected adverse events. Subjects will be contacted by telephone by the study staff once a week during the treatment phases to

review any AEs, and the diary will be reviewed for any recorded AEs on study days 29, 57, and 85.

In order to avoid bias in eliciting AEs, subjects will be asked general, non-leading questions such as "How are you feeling?"

All AEs will be followed until resolution or stabilization of the event. This may require additional clinical assessments and laboratory tests.

7.1.6 Routine Reporting of Adverse Events

AEs, whether or not associated with study drug administration, will be recorded in the source documents.

Follow-up assessments should be repeated to document return of any abnormalities to normal, or to document other outcome of the AE.

7.1.7 Reporting of Serious Adverse Events, Including Death

SAEs, including death due to any cause, which occur during this study or within 30 days following the last dose of the study drugs, whether or not related to the administration of study drugs, will be recorded in the source documents, and on an SAE report. The SAE report will include the following information:

1. Subject identification including subject number, initials, and date of birth;
2. Randomization number;
3. Date of first dose of study drug and details of administration, including study drug name (including labeled strength and manufacturer), lot number, expiration date, and dose;
4. Date of last dose of study drug (i.e., prior to onset of SAE) and details of administration, including study drug name (including labeled strength and manufacturer), lot number, expiration date, and dose;
5. Medical diagnosis of the event in standard medical terminology (if a medical diagnosis cannot be determined, a description of each sign or symptom characterizing the event);
6. Date of onset of the event;
7. Date of resolution of the event (or confirmation ongoing);
8. Severity of the event according to criteria in Section 7.1.2;

9. Assessment of the attributability of the event to the study drug according to the definitions in Section 7.1.3;
10. Why event is considered serious per the definition in Section 7.1.1.2;
11. Whether the event is expected per the definition in Section 7.1.4;
12. Action taken in treating the event and/or change in study drug administration or dose (including concomitant medications or therapies administered, whether hospitalization or prolongation of hospitalization was required, diagnostic procedures performed, and whether the subject was discontinued from the study);
13. All concomitant medications (including doses, routes, regimens, and indications);
14. Pertinent laboratory data;
15. Medical history.

The Investigator will review each SAE report and evaluate the relationship of the adverse experience to study drug and to underlying disease. Based on the Investigator's assessment of the adverse experience, a decision will be made concerning the need for further action. The primary consideration governing further action is whether new findings affect the safety of subjects participating in the clinical trial. If the discovery of a new adverse experience related to the study drug raises concern over the safety of continued administration of study drug, the Investigator will take immediate steps to notify the regulatory authorities. Further action that may be required includes the following:

1. Alteration of existing research by modification of the protocol;
2. Discontinuation or suspension of the study;
3. Alteration of the informed consent process by modification of the existing consent form and informing current study participants of new findings;
4. Modification of previously identified expected adverse experiences to include adverse experiences newly identified as study drug-related.

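### SAEs are to be recorded for 30 days after the last dose, but the last scheduled safety contact is on Day 85, so new-onset SAEs in the window after period 2 have no scheduled ascertainment

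*Combined protocol and SAP*

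**What the plan says.** Section 7.1.7 sets the recording window for serious adverse events: "SAEs, including death due to any cause, which occur during this study or within 30 days following the last dose of the study drugs", regardless of relationship to study drug.

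The scheduled means of finding such events are these:

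- Section 7.1.5: "Subjects will be contacted by telephone by the study staff once a week during the treatment phases", and "the diary will be reviewed for any recorded AEs on study days 29, 57, and 85".
- Section 6.5 (second treatment period): "Subjects or informants will be contacted weekly between study day 57 and 85 for general safety assessments".
- Section 7.1.5 also relies on the subject: "Subjects will be instructed to report all AEs experienced during the study". It does not mention the 30 days after the last dose.
- Section 6.6 ends with the Day 85 assessments, and Day 85 is the last column of Appendix B.

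Section 6.7 says that participation "will be up to 18 weeks (first screening visit through final follow-up visit"). No part of Section 6 or Appendix B defines that final follow-up visit or gives it a date. Known adverse events are followed until they resolve or stabilize (Section 7.1.5).

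**The concern.** Section 7 makes adverse events the main basis for judging safety. A window for serious events is useful only if there is some way to learn of events inside it. Section 7.1.7 defines the window, and the visit schedule stops at about the moment it opens for period 2.

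For a subject who completes both periods, anything that happens in the washout is already during the study. The 30-day clause therefore adds something only after the final dose, and no contact is planned there. The subjects have probable Alzheimer's dementia, so unprompted reporting after the last visit is a weak substitute for a call. At stake is how fully SAEs are found in the month after period 2, including the month after active drug for about half of the subjects.

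**Working it through.** **Inputs**

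- Visits on Days 1, 29, 57 and 85 (Sections 6.3 to 6.6, Appendix B).
- Period 2 dosing starts on Day 57: "The subjects will be instructed to begin the first dose that evening" (Section 6.5).
- Length of dosing: "All subjects will take the study drug (placebo or active) twice a day for 4 weeks" (Section 5.3).
- SAE window of 30 days after the last dose (Section 7.1.7).
- 36 subjects, randomized four at a time to two sequences (Sections 3 and 5.2).
- Participation of up to 18 weeks (Section 6.7).
- Alzheimer's medication stable for at least 30 days before screening and at least 60 days before Day 1 (Section 4.1, criterion 7).

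**1. The plan's own figure.** Day 85 − Day 1 = 84 days, and 84 / 7 = 12.0 weeks. This reproduces the 12-week trial duration in the synopsis.

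**2. Last dose of period 2.** Twice-daily dosing for 28 days from the evening of Day 57 ends on the morning of Day 57 + 28 = Day 85. If the morning dose is not taken on the visit day, the last dose is on Day 84.

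**3. Window after period 2.** It ends on Day 84 + 30 = 114 or Day 85 + 30 = 115. That is 114 − 85 = 29 or 115 − 85 = 30 days after the last scheduled contact. Scheduled contacts in that time: none.

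**4. The same span after period 1.** The last dose is on Day 28 or 29, so 30 days later is Day 58 or 59. The Day 57 visit and diary review cover 57 − 28 = 29 or 57 − 29 = 28 of the 30 days. The remaining day or two fall in period 2, when weekly calls have resumed.

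**5. Subjects affected.** Taking the sequences as equal, 36 / 2 = 18 subjects receive LEV second.

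| 30 days after | LEV | Placebo | Scheduled contact |
|---|---|---|---|
| Period 1 | about 18 | about 18 | Day 57 visit and diary review |
| Period 2 | about 18 | about 18 | none |

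So 18 / 36, or half, of the post-LEV windows have no scheduled contact, and so do half of the post-placebo windows.

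**6. Does a call at Day 115 fit the 18 weeks?** 18 × 7 = 126 days. Day 1 to Day 115 is 114 days, which leaves 126 − 114 = 12 days for screening. A subject whose Alzheimer's medication has been stable for exactly 30 days at screening must wait 60 − 30 = 30 days for Day 1. Screening, trial and window then take 30 + 84 + 30 = 144 days, and 144 / 7 = 20.6 weeks, which is 144 − 126 = 18 days over the limit. If participation ends on Day 85, the same subject needs 30 + 84 = 114 days (16.3 weeks), which fits.

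**The case against.** The best case for the plan has five parts.

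- **Section 7.1.7 is a recording rule.** It says what is done with an SAE that comes to light. It does not promise active questioning to Day 115, and it nowhere claims a complete record. This is fair: a recording window longer than the visit schedule is not in itself a contradiction. The practical gap remains, because the plan gives no scheduled way to learn of the events it undertakes to record.
- **Open events are followed.** A reader might infer that every SAE after Day 85 is captured only if someone volunteers it. The documents do not support that. An adverse event already open at Day 85 is followed until it resolves or stabilizes, so one that turns serious should be found. The gap concerns new-onset SAEs.
- **The treatments are affected alike.** A reader might infer that the uneven follow-up biases the safety comparison. It does not: each period has about 18 subjects on each treatment, so the loss is balanced between LEV and placebo.
- **Section 6.7 may simply mean Day 85.** Criterion 6 of Section 4.1 asks for four in-person days, which matches Days 1, 29, 57 and 85, and Appendix B already uses the word follow-up for a Day 85 rating. The 18 weeks also fit 42 days (6 weeks) of screening plus the 12-week trial. So Section 6.7 does not clearly promise a later contact. It is ambiguous and should say which reading is meant.
- **Late drug effects may be few.** Section 1.2 gives a half-life of 6 to 8 hours and says that the dose needs no weaning. This bears on how much drug-related information the window would yield. It does not remove the gap, because the plan itself chose a 30-day window covering all causes.

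**Conclusion.** The point holds in a limited form. As the plan is written, new-onset SAEs from Day 85 to about Day 114-115 have no scheduled ascertainment, while the equivalent time after period 1 is almost fully covered. The gap applies to every subject who completes period 2. For about 18 of the 36, the uncovered month is the one after LEV.

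This is a modest weakness in safety ascertainment that is cheap to repair. It does not touch the efficacy analysis, the sample size or the error rates, and it gives no reason to expect the LEV-placebo comparison of adverse events to be distorted.

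The conclusion assumes roughly equal sequence groups, with similar completion, and dosing for the full 28 days. It is also confined to the text supplied: some material between Sections 6.7 and 7 was not available, and nothing is inferred from its absence. Appendix B was available and ends at Day 85.

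**What to change.** Add one telephone safety contact for each remaining subject at the end of the 30-day window that the protocol already states. Existing staff would make it, using the non-leading question in Section 7.1.5, and it would appear as a line in Appendix B. Align Sections 6.6, 6.7, 7.1.5 and 7.1.7 with it, and extend the reporting instruction to subjects so that it names the same window.

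In Section 6.7, state whether the final follow-up visit is Day 85 or this call. If it is Day 85, the 18 weeks can stand. If it is the call, restate the 18 weeks to allow for the 144-day (about 20.6-week) path.

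The cost is up to 36 short calls by staff who already make weekly calls, and a minor amendment that needs IRB approval (Sections 13.3 and 15). The Version 3 summary of changes refers to subjects already enrolled, so fewer than 36 calls may still be possible.
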